Tuberculosis is also a major cause of morbidity and mortality among children: in 2016, 1,000,000 children became ill from TB, of which 250,000 died -80% of them were under 5 years old (2). Childhood TB has been a largely neglected subject for organizations dedicated to TB or child health.

Active TB in children is also a serious and frequent co-infection of HIV or a co-morbidity of malnutrition in endemic environments (3-6). Malnutrition is an independent risk factor for both development of TB and mortality due to TB (7-9), and is associated with more severe forms of TB (8). It is essential to better integrate the diagnosis of tuberculosis into vertical programs for non-infectious diseases, especially for malnutrition services (5,6,10,11).

b. TB diagnosis in children

According to WHO, the TB diagnostic gap world-wide is still enormous: 39% of all patients suffering from TB remained undiagnosed in 2016 (1). This gap is even higher when it comes to paediatric TB. In some African settings, only 20% of estimated cases were diagnosed (12).

The diagnosis of tuberculosis in children is particularly difficult and is essentially based on clinical symptoms. TB scoring systems have not proven to be effective and young children have difficulty expectorating adequate samples for microbiologic investigation. Even if samples are obtained by partly invasive procedures such as naso-pharyngeal aspiration or gastric lavage, the positivity rate in smear or culture is low (13,14). Similarly, radiographs and skin tests of tuberculin give only very limited information in children and are rarely available in contexts where Médecins sans Frontières (MSF) works.

In addition, TB cultures and Xpert MTB / RIF® (Cepheid, Inc.) are often not available in endemic areas. Traditionally, TB culture has been considered as the gold standard for TB diagnosis. However, access to culture and time till final result make culture not feasible as a regular test in most of the contexts where MSF works. This is the reason why an international expert panel established that the case definition of “confirmed tuberculosis” includes a positive WHO-endorsed nucleic acid amplification test (Xpert MTB/RIF) in addition to culture confirmation using a valid respiratory specimen for microbiologic examination, irrespective of the culture result (13).

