According to National TB Program data, in 2018 2200 persons were started on TB treatment and 45% among them were ≤ 15 years old.

MSF OCBA launched the permanent mission in Guinea Bissau (figure 2) in 2016 as a strategic choice with the objective to test and develop innovative medical strategies in paediatric care to decrease childhood mortality and which will ultimately help to overcome operational challenges, by being capitalized and exported to more unstable settings. MSF supports several departments in the Simão Mendes National Hospital in collaboration with MoH: paediatric intensive care unit (PICU), neonatal intensive care (NICU), in-patient therapeutic feeding centre (ITFC) and few beds in the paediatric ward. MSF is currently diagnosing TB in children and referring them to MoH / National TB program to initiate and continue treatment.

Figure 2:

6. Objectives

a. Main objective

To determine the sensitivity and specificity of Xpert MTB/RIF Ultra in stool and urine samples in suspected paediatric TB cases in comparison with the WHO recommended test (Xpert MTB/RIF Ultra in sputum sample or validated extrapulmonary sample).

b. Secondary objective

- 1) To determine the sensitivity and specificity of Xpert MTB/RIF Ultra rifampicin resistance using stools and urine in pulmonary and extra pulmonary TB confirmed and unconfirmed TB cases as a composite.
- 2) To disaggregate according to HIV status (positive, negative) and to nutritional status (SAM or not).
- 3) Describe the prevalence of positive TB LAM in HIV-infected, HIV-uninfected and SAM patients with and without TB.

7. Patients and Methodology

a. Study design

We plan to conduct a multicentric study in 2 different centres: Malakal (South Sudan) and Bissau (Guinea Bissau). The methodology for the evaluation of Xpert MTB/RIF Ultra in stools and urine will be a cross-sectional study.

b. Study sites

This study will be conducted in South Sudan in two different sites, the Malakal POC and the Malakal town, and in Bissau in one site, the Simão Mendes National Hospital.

c. Partnership and study coordination

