- Persistent fever ($>38^{\circ}\text{C}$) beyond one week after exclusion from classical causes such as malaria or pneumonia
- Persistence or aggravation of fatigue
- Chest radiographs imaging suggestive of tuberculosis

4. Case with diagnosis of tuberculosis (40,41)

- **Confirmed TB:** patients with Xpert MTB/RIF Ultra positive (or TB culture positive when available) in a respiratory sample (pulmonary TB) or in other sample, such as CSF, lymph node or other tissue/liquid (extra pulmonary TB); TB LAM positive in HIV-infected patients.
- **Unconfirmed TB:** no microbiological confirmation but clinical diagnosis of TB and started on anti TB treatment (as established in Appendix 5).
- **Unlikely TB:** good response to other treatments (antibiotic, nutritional support, etc.) and no suggestive symptoms after 1 week of admission and until the 2 month follow-up.

8. Study procedures

a. Identification of participants

Eligible children will be identified upon admission to paediatric ward, ITFC, PICU/NICU (in Bissau) or as suggestive cases in OPD. The identification of suspected TB cases will be mainly based on clinical criteria. A diagnostic algorithm (Appendix 4) will be applied to all suspected cases. The populations of interest for this study are hospitalized children, severely malnourished (SAM) and HIV positive or exposed children.

b. Laboratory

1. Sample collection

All patients included in the study will have requested one stool and one urine sample. The team will follow a specific SOP for respiratory sample collection (naso-pharyngeal aspirate, gastric lavage or spontaneous sputum), stools, urine and lymph nodes (or other validated extra pulmonary samples) as described in the appendixes. In hospitalized children, all samples will be collected during hospitalisation and patients not capable of producing the required sample (stools/urine) during this period will be excluded from the study. For ambulatory patients, samples will be collected within 2 hours and, if child not capable of producing stools/urine, samples will be requested to be brought by parents or guardians the day after.

2. Laboratory procedures

Xpert MTB/RIF Ultra will be performed to respiratory or extra pulmonary validated samples, stools and urine for all patients at baseline, and for those with negative results and persistent symptoms, will be repeated after 1 to 2 weeks.

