TB LAM in urine will be tested in all Malakal patients (starting from November 2021) and the result (negative/positive and grade 1-4) recorded in the CRF Lab form. The result will be shared with Research Manager who will only communicate to clinicians in case of HIV-infected patient; in these patients, TB LAM will be used as per clinical protocol.

3. Sample handling and storage

Respiratory specimens will be collected at the clinic and samples will be kept between 2 and 8°C until processed. Processing will be done within the 24 hours and not more than 72 hours after collection. A sterile stool container and instructions will be provided to the parent or guardian for specimen collection and handling. Following delivery to the laboratory, the stool specimen will be kept in a cool dry place and processed within 2 hours. Samples obtained in this study will adhere to all local laboratory procedures governing the storage of biological specimens.

c. Linkage to care for HIV/TB patients

All patients HIV positive will be enrolled into **HIV care** either in MSF program (Malakal) or MoH programs (Bissau). MSF will guarantee that all children will be started on ART after 2 weeks of TB treatment (or as soon as possible if TB has been excluded) or differed to 4-6 weeks in case of TB meningitis.

All TB cases (confirmed or unconfirmed) will be enrolled in **TB care** in MSF program (Malakal) or MoH program (Bissau). MSF will ensure all patients to be started on adequate weight-based dose fix combinations and followed up during the length of treatment. All children diagnosed of DRTB will be initiated on DRTB treatment regimen according to national recommendation.

In patients where stool samples yield positive results and sputum tests are negative, stool results will be communicated to Study Coordinator on site for interpretation and appropriate clinical management. Where stools results are concordant with sputum results, no additional information will be provided.

As a transversal study, it is not foreseen to follow-up patients for study purposes. The follow-up will be required though for the study “Evaluating POCUS to improve TB diagnosis in children”.

d. Data collection

The following information will be noted in an individual case study report form (CRF) for each participant:

1. DEMOGRAPHIC INFORMATION AND INFORMED CONSENT OF PATIENTS:

- Study code
- Date of birth / age
- Sex
- Parent or guardian's informed consent: Yes / No

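### If objective 3 uses the section 7.e.4 TB classes, LAM prevalence in HIV-infected children without TB is 0% by definition, whatever the true rate

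*Combined protocol and SAP*

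**What the plan says.** Secondary objective 3 (sections 1 and 6.b) is to "Describe the prevalence of positive TB LAM in HIV-infected, HIV-uninfected and SAM patients with and without TB". Neither section says which TB definition makes that split, and section 10 (Data Management and Analysis) does not mention LAM.

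Section 7.e.4 sorts participants into three classes. Confirmed TB is a positive Xpert Ultra, or a positive culture where available, on a respiratory or other sample; the same entry adds "TB LAM positive in HIV-infected patients". Unconfirmed TB is "no microbiological confirmation but clinical diagnosis of TB and started on anti TB treatment". Unlikely TB rests on a good response to other treatment and the absence of suggestive symptoms.

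The main objective (section 6.a) uses a reference without LAM: "Xpert MTB/RIF Ultra in sputum sample or validated extrapulmonary sample". The plan does not say that objective 3 uses it.

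Under section 8.b.2, LAM is done in all Malakal patients from November 2021. On the use of the result it says: "The result will be shared with Research Manager who will only communicate to clinicians in case of HIV-infected patient". It also says that the result is "recorded in the CRF Lab form".

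**The concern.** Objective 3 asks how often LAM is positive in children with TB and in children without it. When a positive LAM is itself enough to put an HIV-infected child in the TB group, the test result helps to define the group in which it is then described. Every LAM-positive HIV-infected child leaves the without-TB group, so that cell must be zero.

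LAM is not a criterion in HIV-uninfected children, so their without-TB figure is a real observation. The two would appear side by side, one measured and one fixed by definition, and a reader could take the contrast as evidence that LAM is perfectly specific in HIV-infected children. The with-TB figure is biased upward whenever a LAM-positive child would otherwise have been classed without TB. The severely malnourished group is affected only through its HIV-infected members.

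**Working it through.** The plan gives no LAM prevalence, LAM sample size or LAM precision, so there is no stated figure to reproduce.

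**1. The logic.** Among HIV-infected children, let D be TB by criteria other than LAM (Xpert, culture, or clinical diagnosis with treatment) and L a positive LAM. Under section 7.e.4, with TB = D or L, and without TB = neither D nor L. Let p = P(D), s = P(L given D) and f = P(L given not D).

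- P(L given without TB) = 0 for every f.
- P(L given with TB) = [p·s + (1−p)·f] / [p + (1−p)·f], which exceeds s whenever f > 0 and s < 1.

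With assumed p = 20%, s = 30% and f = 10%: (0.06 + 0.08)/(0.20 + 0.08) = 50% with TB and 0% without. Classes that ignore LAM give 30% and 10%. The zero is the same whether without TB means Unlikely only or Unlikely plus Unconfirmed.

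**2. Size of the stratum.** Section 7.d.4 plans 143 children in Malakal. Section 5.a gives HIV prevalence of 2.7% (country and region) and 11% co-infection in Malakal. Neither figure is for children with presumptive TB, so applying them is an assumption.

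- All 143 tested: 143 × 0.027 = 3.9 to 143 × 0.11 = 15.7, or about 4 to 16 children.
- Half tested: 1.9 to 7.9. A quarter tested: 1.0 to 3.9.
- If the section 12 phases run in sequence, inclusion ends after 2 + 1 + 24 = 27 months from January 2019, in March 2021. The section 1 timeframe ends in July 2021. Both precede November 2021, so on schedule no child would be tested. Section 11.d allows for longer recruitment.

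**3. Illustration at the ceiling (all counts assumed).** Take 16 HIV-infected children: 3 Xpert-positive (1 LAM-positive) and 13 Xpert-negative (2 LAM-positive), with 6 of the 13 treated on other clinical grounds. Treatment without Xpert confirmation is plausible, because the background section on TB diagnosis in children calls it "particularly difficult and is essentially based on clinical symptoms". Let k be the number of the 2 LAM-positive Xpert-negative children who are among those 6.

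| k | With TB, LAM ignored: (1+k)/9 | With TB, as written: 3/(11−k) | Rise (points) | Without TB, LAM ignored: (2−k)/7 | Without TB, as written |
|---|---|---|---|---|---|
| 0 | 1/9 = 11% | 3/11 = 27% | 16 | 2/7 = 29% | 0/5 |
| 1 | 2/9 = 22% | 3/10 = 30% | 8 | 1/7 = 14% | 0/6 |
| 2 | 3/9 = 33% | 3/9 = 33% | 0 | 0/7 = 0% | 0/7 |

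The exact upper 95% limits for 0/5, 0/6 and 0/7 are 1 − 0.025^(1/n) = 52%, 46% and 41%. A split by Xpert gives 1/3 and 2/13 (15%, exact 95% CI 2% to 45%) in every row.

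**4. Chance that any child is moved.** At the plan's 20% Xpert positivity, about 3 to 13 of the 4 to 16 children are Xpert-negative. Assume half are treated anyway. The chance that at least one is LAM-positive and not otherwise treated is 1 − (1 − r/2)^n for LAM rate r. At r = 5% this is 1 − 0.975^3 = 7% to 1 − 0.975^13 = 28%. At r = 15% it is 1 − 0.925^3 = 21% to 1 − 0.925^13 = 64%.

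**5. Severely malnourished children.** With an assumed 11% HIV-infected share h and f = 10% throughout, the observed without-TB rate is (1−h)f / [(1−h) + h(1−f)] = 0.089/0.989 = 9.0% instead of 10%.

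**The case against.** The zero depends on two things that the plan leaves unstated: that objective 3 uses the section 7.e.4 classes, and that Confirmed takes precedence. The Unlikely TB text does not require a negative test, so a LAM-positive child who improves on antibiotics fits both classes literally. The variable actually recorded is a discharge diagnosis on the clinical form (Appendix 4), which does not mention LAM. The practical effect may be nil: if a quarter of the children are tested, the chances in step 4 fall to about 2% to 8% and 6% to 22%. Section 10 already promises 95% confidence intervals, and upper limits of 41% to 52% hardly suggest perfect specificity. An Xpert split has its own cost: the background reports pooled sensitivity of 62% to 66% against culture for conventional Xpert on respiratory samples, so some true TB would be counted as Xpert-negative.

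The points about size stand, and so does the cost of the split. The points about the definition do not remove the problem. The overlap between Confirmed and Unlikely applies equally to an Xpert-positive child, and the ordinary reading settles it in favour of Confirmed. The discharge form uses the Confirmed and Unlikely labels without offering another definition. Wide intervals around a zero do not help when the zero is not an estimate.

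**Conclusion.** The concern holds. Under the only TB classification that the plan gives for participants, LAM prevalence in HIV-infected children without TB is 0% at any true rate, and the with-TB prevalence is overstated whenever LAM alone moves a child into the TB group. In the assumed illustration the overstatement is 16, 8 or 0 points.

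The zero is certain once objective 3 uses these classes with Confirmed taking precedence. Its practical weight is uncertain: it concerns one stratum of a descriptive secondary objective, about 4 to 16 children at the ceiling and possibly none. It should be corrected before analysis because the figure would be wrong by construction and the correction is cheap.

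**What to change.** State in section 6.b or section 10 that, for objective 3, TB status is Xpert Ultra (or culture when available) positive versus negative on respiratory or validated extrapulmonary samples, without LAM. Show Xpert-negative children treated as Unconfirmed TB in a separate row and flag those whose only positive result is LAM. Note that in HIV-infected children this row is still influenced by LAM, because clinicians see the result; deleting the LAM clause alone would not remove the circularity. Report counts with exact 95% confidence intervals among LAM-tested Malakal children.

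For consistency, state in section 7.d.4 that the primary analysis uses the section 6.a reference and not LAM, and reconcile the November 2021 LAM start with the section 1 timeframe and section 12. Clinical use of LAM is unchanged.

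The cost is analysis wording and no new tests. One check is needed: the laboratory form as reproduced in Appendix 17 and the data list in section 8.d show no LAM field, so one may have to be added. The downside is that LAM-only children no longer count as confirmed in this analysis, clinically diagnosed children fall outside the Xpert-positive group, and the HIV-infected cells stay small.

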In South Sudan, this study will be conducted in partnership between Médecins sans Frontières Operational Centre Barcelona-Athens (OCBA) and the Ministry of Health of South Sudan, in collaboration with the National TB Program. The MoH is willing to provide administrative and political support. The Xpert MTB/RIF Ultra machine was procured by MoH as well. No academic institutions have been involved in the study.

In Guinea Bissau, this study will be conducted in partnership between MSF OCBA and the MoH of Guinea Bissau, in close collaboration with the National TB Program. MSF works closely with MoH in Simão Mendes hospital, and the General Director of the TB hospital (Raoul Follereau Hospital), as well as the Responsible of the TB ambulatory care at Simão Mendes, are co-authors of the study and willing to provide technical support.

d. Study participants and sample size

1. Research population

The research population are children with presumptive TB in (Malakal town and POC hospitals) or in Bissau (Simão Mendes National Hospital).

Note that the same population will be offered to participate in the study “Evaluation of point of care ultrasound (POCUS) for the diagnosis of TB in children” (ref: MSF ERB 18116) which will be submitted in a separate protocol. Note that all participants will be asked to sign 2 separate consent forms.

2. Participants: inclusion criteria

- Any child from 6 months of life to 15 years old
- TB suspected according to diagnostic criteria
- Informed consent provided by legal responsible or companion

3. Participants: exclusion criteria

- Patients who have received TB treatment for > 1 day in the last 3 months
- Patients not producing stools during period of hospitalization

4. Sample size

The primary analysis will be to describe the performance of Xpert MTB/RIF Ultra from stools and urine in patients with confirmed TB. The estimated total sample size is **327 suspected TB patients: 143 in Malakal and 184 in Bissau**. The sample size difference is justified by the number of suspected patients currently consulted in both settings. Note that this is the same sample size

that will be used for the study “Evaluation of point of care ultrasound (POCUS) for the diagnosis of TB in children”.

The sample size has been estimated with a variety of assumptions: we assume that sensitivity of Xpert MTB/RR in stools and urine will be 60% and specificity 95%.

Expected sensitivity	Precision			
	0.05	0.07	0.1	0.12
0.5	385	196	97	67

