Angular deformation of the spine (gibbous)	
--	--------------------------

Lymphadenopathy	
Subacute meningitis	
Abdomen distended with ascites	
> 2 weeks of diarrhoea	
Painless enlarged joints	
Pleural effusion	
Other	 Specify: _____
POCUS done:	Yes  No 
	Date: / /

Information at discharge: final diagnosis **Date:** / /

Confirmed pulmonary TB	
Suspected pulmonary TB	
Confirmed extra pulmonary TB	
Suspected extra pulmonary TB	
Unlikely TB	
Other	 Specify: _____

TB treatment

Started: Yes No Date ATT started: / /
 Regimen: _____

Follow-up after 2 months of discharge (POCUS participants) **Date:** / /

Nutritional status:	Not significantly malnourished 	MAM 	SAM 
TB treatment prescribed:	Yes 	No 	
Under TB treatment:	Yes 	No 	
If interruption, specify reason:			
Smear at month 2:	Done 	Positive 	Negative 
Not done 			
POCUS done:	Yes  No 	Date: / /	

[figure not shown]
TB patients: follow-up after 6 months of discharge (POCUS participants) **Date:**
 / /

Nutritional status:	Not significantly malnourished 	MAM 	SAM 
TB treatment finalised:	Yes 	No 	
Smear at month 6:	Done 	Positive 	Negative 
Not done 			
POCUS done:	Yes  No 	Date: / /	

TB treatment outcomes:

Cured:		Defaulted:		Date: /
/				
Completed:		Death:		
Failure:		Not evaluated:		

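### Unlikely TB is defined by a symptom-free course to 2 months, which this study does not follow and its clinical form cannot record

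*Combined protocol and SAP*

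**What the plan says.** Section 7.e.4 sorts children into confirmed, unconfirmed and unlikely TB. The third class requires a good response to non-TB treatment and also "no suggestive symptoms after 1 week of admission and until the 2 month follow-up".

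Section 8.c states: "As a transversal study, it is not foreseen to follow-up patients for study purposes". It then points to the companion study: "The follow-up will be required though for the study" of POCUS. Section 7.d.1 describes the overlap between the two: "Note that the same population will be offered to participate in the study", and "Note that all participants will be asked to sign 2 separate consent forms".

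The two studies share one clinical form (Appendix 4). The *Unlikely TB* box sits in the block headed "Information at discharge: final diagnosis". A later block is headed "Follow-up after 2 months of discharge (POCUS participants". It asks about nutritional status, TB treatment prescribed and under way, the reason for any interruption, smear and POCUS. Section 8.d lists the final diagnosis among the baseline items.

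Two secondary objectives in section 6.b bear on the point. The first concerns rifampicin-resistance accuracy "in pulmonary and extra pulmonary TB confirmed and unconfirmed TB cases as a composite". The third describes LAM positivity in children with and without TB.

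**The concern.** The label is given at discharge, but one of its criteria is not settled until about 2 months. Followed as written, a child is called *Unlikely TB* before the definition can be met, and nothing on the form confirms or reverses the label later. What remains at discharge is largely the response to other treatment, and Appendix 5 (note f) itself says that a response to antibiotics does not exclude TB and that the child should stay under follow-up.

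At stake is the make-up of any non-TB group. A child whose TB shows itself after discharge would stay in that group. A true positive index result in such a child would then be read as a false positive, and a positive LAM as LAM positivity without TB.

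**Working it through.** **1. The plan's own figures.** With sensitivity 60%, precision 12% and a 95% interval, n = 1.96² × 0.6 × 0.4 / 0.12² = 64.02, stated as 64. Then 64 / 0.20 = 320, and 320 / 0.98 = 326.5, stated as 327. These reproduce, so the sample size is not in question. They imply 320 − 64 = 256 children without confirmed TB.

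**2. Each part of the definition against where it could be recorded.**
- *Response to other treatment:* can be judged by discharge.
- *No symptoms from 1 week after admission:* inpatients have an admission date. Outpatients, who are enrolled under section 8.a and observed for 2 hours under section 8.e, do not.
- *No symptoms up to 2 months:* this study has no visit (section 8.c). The form has a block for POCUS participants only, with no symptom item.
- *Final class after 2 months:* no field. The only diagnosis entry is at discharge.

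On the form shown, the third part cannot be documented for any child, whether in POCUS or not.

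**3. How many children might lack a 2-month visit.** The documents give no share of unconfirmed TB (u), POCUS co-enrolment (c) or 2-month retention (r), so these are assumptions: u from 0 to 30%, c from 50 to 100%, r from 80 to 100%.
- Candidates for the non-TB group: 256 × (1 − u), from 179 to 256.
- Without a visit: 256 × (1 − u) × (1 − c × r). With u = 0 and c = r = 0.9, 256 × 0.81 = 207 have a visit and 49 do not. The extremes are 0 (c = r = 1) and 256 × (1 − 0.5 × 0.8) = 154.

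**4. What misclassification would do to a specificity, if one were computed on this group.** Let f be the share of the group that truly has TB and s the share of those who are index-positive. Apparent specificity = (1 − f) × 0.95 + f × (1 − s). The 95% is the assumption in section 7.d.4; f is assumed; s is taken as 0.5 to 0.6.
- f = 2%: 0.931 + 0.008 to 0.010 = 93.9-94.1%
- f = 5%: 0.9025 + 0.020 to 0.025 = 92.3-92.8%
- f = 10%: 0.855 + 0.040 to 0.050 = 89.5-90.5%

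**The case against.** The strongest reply is that the follow-up exists, but in the companion study. The same children are offered POCUS, the planned sample size is the same, and the form is shared. Its 2-month block records TB treatment prescribed and under way, which would pick up many children whose TB was recognised after discharge. Section 8.b.2 repeats Xpert after 1 to 2 weeks in negative children with persisting symptoms, and section 10 promises data from programme follow-up. The POCUS protocol is not among the documents and may collect symptoms. This stands to the extent that a reader should not infer that no child can ever be classified. It does not close the gap: POCUS needs its own consent, no rule links its 2-month data to the classification here, and the sentence in section 10 names no symptom item, time point or classification rule.

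A reader might also infer that the study's headline specificity is at risk. It is not. The main objective uses Xpert Ultra on sputum or a validated extrapulmonary sample as reference, and *Unlikely TB* plays no part in it.

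Nor do the documents say that *Unlikely TB* is the comparator for the composite. That objective is worded for rifampicin resistance and names only the TB side. The LAM objective describes prevalence rather than specificity, and LAM is tested only in Malakal.

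Finally, the 60% sensitivity was set for confirmed TB, and nothing supports carrying it over to children without confirmation. Children positive on stool but negative on sputum are referred to the Study Coordinator (section 8.c). Some may be treated and so leave the *Unlikely TB* group, which would shrink the effect for stool. Both objections to the size stand.

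**Conclusion.** The contradiction between sections 7.e.4 and 8.c and the Appendix 4 form is real: one criterion of *Unlikely TB* cannot be documented on the form shown, and its 1-week clause does not fit outpatients. The consequence is confined to secondary analyses that need a non-TB group. It is clearest for LAM, where the group without TB is required but not defined. Since LAM-positive HIV-infected children count as confirmed TB under section 7.e.4, the effect there falls mainly on HIV-uninfected children, including those with severe acute malnutrition. For a specificity against confirmed plus unconfirmed TB, dependence on *Unlikely TB* is an inference: it is the only non-TB class that section 7.e.4 defines.

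The direction of any error is clear if children with later-recognised TB stay in the group. Its size is unknown. The specificity figures above are hypothetical and do not apply to LAM, and the count of children without a visit rests on assumed enrolment and retention. The point is worth correcting but does not threaten the main result.

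**What to change.** Reconcile sections 7.e.4 and 8.c with Appendix 4:
- Treat the discharge diagnosis as provisional.
- Add a TB-symptom item and a revised-classification field to the existing 2-month block.
- State that POCUS 2-month data, including TB treatment prescribed, are linked to this dataset and used to assign the final class.
- For outpatients, count the 1-week criterion from enrolment.
- Define which children count as without TB in the LAM analysis, and state the comparator for any specificity against the composite.
- Flag children with no 2-month visit as not verified at 2 months, and report the secondary results both with and without them.

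Dropping the unverified children outright would be a poor default. It would select on a second consent and on retention, both of which may relate to how ill the child was; keeping them rests on the discharge label alone. Reporting both shows whether the choice matters.

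The cost is one or two form items on a visit that already exists, some wording, and one extra analysis. Verification still depends on POCUS consent and attendance, so some children will remain unverified.
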